The process for titrating study medication at the initiation of study treatment and for maintaining them during the course of the study will be based on real or simulated plasma levels. To ensure local site blinding and standardization of measurements, some blood samples will be sent to a Central Laboratory for analysis. Lithium levels, TSH, T4, and creatinine will be analyzed by the Central Laboratory, while other samples, for complete blood count (CBC) and electrolytes will be sent to the local VA laboratories for analysis.

Lithium levels, creatinine, eGFR, and summary of side effects will be sent to the MAVERIC data coordinating center which will send real or simulated plasma levels and dosage adjustment recommendation to the Site Physician and to the Central Psychiatrist/Safety Officer. A lithium level of 1.2 or above will be considered a potentially dangerous situation and will be automatically sent to the Site Physician as well as the Coordinating Center and Central Psychiatrist/Safety Officer.

The Site Physician will use these levels and a check list review of symptoms at the time of the blood draw to make dose adjustments. During the initial dose adjustments, the Site Physician will typically decide between increasing doses by one pill per day, or maintaining the current dose.

Participants will have titration visits until they reach the target steady state: a serum lithium level between 0.6 and 0.8 mEq/L, over 2 consecutive visits, at the same dose, and with the second level the same or 0.1 mEq/L lower than the first level. It is expected that most patients will titrate within 4-6 visits, but the process may take fewer visits, or may take up to 8. If steady state is not achieved after 8 visits, the Central Psychiatrist/Safety Officer will work with the site on a case-by-case basis to determine a prescribing plan. If participants are not able to tolerate the dose needed to achieve the target level, they will be prescribed their maximum tolerated dose.

If it has been fewer than 60 days from randomization to achieving steady state, the participant's next visit will be a steady state follow-up visit 2 months after randomization (within the window allowed for steady state visits). If it takes more than 60 days, the next visit will be the 3 month steady state visit, and the month 2 visit will be omitted.

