In general, blood samples, updated medical and psychiatric history, and review of side effects will be obtained on approximately the 7th day (\pm 2 days) of the dosing interval (see section XIV, Titration Visits, for more detail). Findings will be reported to the Central Psychiatrist/Safety Officer and lithium levels (actual or simulated) under ideal circumstances will be communicated to the site within 48-72 hours.

Once the Site Physician decides on dose adjustments and orders the study medication, the blister card containing the prescribed amount of tablets will be dispensed in person or by express mail.

If, for any reason, the scheduled blood tests are missed, the process for dose adjustment will need to be modified. However, the scheduled assessments will still be completed to guide patient management as well as to ensure ongoing study assessments. The Site Physician may either hold the current dose if there are problems or continue the current dose but may not, to be cautious, increase the dose. If necessary, the subject will be mailed enough blister-packed tablets to cover the time until the next scheduled dose adjustment.

Ongoing dose adjustments

During the course of double-blind treatment a number of events may indicate the need for additional clinical assessments, blood level determinations, other laboratory tests, and, possibly, dose adjustments. These may, for example, include reports of side effects, observations of possible adverse reactions, laboratory measures, changes in medical status, or modifications in medications. When these occur, the Site Physician will conduct clinical evaluations, obtain blood for lithium level and other determinations as needed using the same procedures for planned dose adjustments. Decisions about clinical management of dosing will be the responsibility of the Site Physician. He or she may ask the patient not to take study medications for up to three days, modify the dose on a temporary basis, or modify the dose from that time onward. In general, he or she will continue to monitor the patient with repeated contacts, assessments, blood levels, and other tests as appropriate until the patient's medical status and blood levels stabilize.

Enhanced usual care for preventing suicide

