All participants will be followed from randomization until the completion of the study (one year of lithium/placebo treatment). Participants will be followed as described in the Schedule of Visits (Table 6). Study assessments will be done at screening, baseline, every 10-14 days during the titration phase (in general, for up to six visits), and monthly until the end of study.

During the titration phase, participants will take the same dose of study medication for a minimum of 5 days prior to having their levels reassessed. Results from the blood draw are available to sites within approximately 3 days of the blood shipment, at which point a new dose may be selected and shipped to the participant if they are unavailable to pick up the prescription. Based on the dispensing of 2 weeks of study medication at a time and that it is necessary to allow a minimum of 4 days after a study visit for processing blood samples, communicating findings to the Central Psychiatrist/Safety Officer, communicating actual or simulated plasma levels to the study site, prescribing, and dispensing medications, there is a window of 10 to 14 days between titration visits. The Site Coordinator can conduct all assessments unless a physical exam is

required. Additionally, it is possible for participants to have unscheduled check-in visits at any time.

During titration phase, each new dose of study medication must be taken for a minimum of five days before collecting and sending another Lithium blood sample.

Steady State Visits

Once participants have reached steady state, study visits will occur every month, with a window from one week before the target date to one week afterwards. For the completion of the study, the window will be between one week before the target date to one month afterwards.

Ongoing Considerations and Special Circumstances

Additional visits will be completed as necessary for emergent events.

Pregnancy testing: At every visit post-randomization, participants of childbearing potential will be reminded of the potential dangers of lithium during pregnancy, review acceptable birth control methods, document what method of contraception is being used, and update all medications as well as over-the-counter medications, supplements being used.. If there is reason to doubt the participant's judgment, a pregnancy test will be done. Women of childbearing potential will have pregnancy testing at each study visit.

Participant Pregnancy:

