Notification of Local Hospital Leadership	Site Study Staff	HIPAA, VHA Directive 1605.01, VHA Handbook 1200.05, Certificate of Confidentiality	Remind local hospital leadership that release of information regarding study-related matters, including unblinding, with any persons outside the study team is prohibited.
Disclosure of information about mental health care, but not information about research participation , to the family	Mental Health Provider (Note: this activity occurs outside of the study protocol, but is provided as a recommendation).	HIPAA, VHA Directive 1605.01, Certificate of Confidentiality	Local policies and procedures will vary. Consult Privacy Officer and other hospital leadership. Provide forms and assist family in completing the forms to facilitate their information seeking. Do not provide any information regarding study-related matters, including unblinding, with any persons outside the study team.

PROCEDURES

Activity	Responsible Party	Considerations/ Requirements	Recommendation
Completion of SAE forms	CSPCRPCC Study Staff	Protocol	Any other outstanding SAE forms should be closed out with the resolved option.
Completion of study forms	Site Study Staff	Protocol	Complete end of study form
Study visit entry into CPRS	Site Study Staff	Protocol, VHA Handbook 1200.05, Certificate of Confidentiality	-Include clinically relevant information (e.g., "participant expired") -Do not to include information about the study (e.g., "participant completed suicide") -Cause of death should be ascertained by medical records and/or death certificate (should not entered into CPRS, should be entered into DataLabs)

Determination of lithium levels: Close surveillance is essential to patient safety. This includes determination of lithium levels, renal function, thyroid function, hematological measures, electrolytes, and electrocardiograms (EKGs) and meticulous attention to concomitant drugs which might increase toxicity. Our protocol meets or exceeds published guidelines for monitoring patients on lithium.

QT Corrected (QTc) Interval: Due to potential lengthening of the QTc, all randomized participants will receive an electrocardiogram (EKG) on a minimum of four study time points:

1. at screening,
2. once during the titration phase,
3. once during steady state, and
4. at the end of study or early termination.

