				T 1	T 2-3	T 4	T 5-6	M 2-5	M 6	M 7-8	M 9	M10,11	Early D/C			
Estimated time per visit	2 hrs	2 hrs	1.25hrs	1hr	45min	1.25hr	45min	1hr	1.25hr	1hr	1hr	1hr	1hr	1.75hr	1.75hr	30min
Phone contact allowed ⁺								Yes		Yes		Yes				Yes
Eligibility Screening																
Informed Consent ⁺⁺	X	X														
Review Incl/Excl. Criteria (S12)	X	X														
Demog. and military history (B02, B03)		X														
Medical history reviewed (B04)			X													
Psychiatric history reviewed (S01)	X		X													
Medications and treatments reviewed (S03)	X	X	X	X	X	X	X	X	X	X	X	X	X	X	X	X
MH Provider concurrence documentation obtained	X	(X)														
Primary Care Provider awareness documentation obtained ⁺⁺⁺	X	(X)														
Medical Assessments																
Physical Exam (B01)		X												X	X	
Vital Signs (B01, T04)		X	X	X	X	X	X	X	X	X	X	X	X	X	X	
EKG ⁺⁺⁺⁺ (S09)		X		X (once during titration)				X (once during steady state)						X	X	
Creatinine (S10, T02)		X		X	X	X	X	X	X		X			X	X	
CBC, electrolytes, calcium (S10, T01)		X				X			X					X	X	
TSH, T4 (S10, T02)		X				X			X					X	X	
Pregnancy test as appropriate (S10, T01)		X	X	X	X	X	X	X	X	X	X	X	X	X	X	
Interim history (B05)			X	X	X	X	X	X	X	X	X	X	X	X	X	X
Enrollment																

Randomization (S12)			X												
---------------------	--	--	---	--	--	--	--	--	--	--	--	--	--	--	--

Study Medication	Eligibility Evaluation	Eligibility Confirmation	BL	T 1	T 2-3	T 4	T 5-6	M 2-5*	M 6	M 7-8	M 9	M 10-11	Early D/C	End of Study	F/U (30 days)
Lithium level (T02)				X	X	X	X	X	X		X				
Adherence (T03, T05)				X	X	X	X	X	X	X	X	X	X	X	
Adverse events, (SAEs and AEs) (using lithium side effects checklist) (B13, T02)			X	X	X	X	X	X	X	X	X	X	X	X	X
Planned dose adjustment				X	X	X	X								
Dispense study medication++++			X	X	X	X	X	X	X	X	X	X	(X)	(X)	
Current Treatment Info.															
Medications (S03)	X		X	X	X	X	X	X	X	X	X	X	X	X	
VA record review	X		X	X	X	X	X	X	X	X	X	X	X	X	X
Service use based on the Cornell Service Index (B05)			X	X	X	X	X	X	X	X	X	X	X	X	X
Psychiatric Measures															
MINI (S11)	X														
PCL (B12)		X													
SCID SUD (S05)	X														
OMC (S06)	X														
UBACC (S04)	X														
CSSRS-lifetime version suppl with SIS for index attempt (S07, S08)	X														
CSSRS-last visit version supple with SIS f/u for attempts (B06, S08)		X	X	X	X	X	X	X	X	X	X	X	X	X	X
PHQ-9 (B07)			X	X		X		X	X	X	X	X	X	X	X
ISS (B08)			X	X		X		X	X	X	X	X	X	X	X
Audit C (B09)			X	X				Month 3	X		X		X	X	

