Buss-Perry (B10)			X												

Barratt (B11)			X											
---------------	--	--	---	--	--	--	--	--	--	--	--	--	--	--

- + During months 2-5, if participants have completed titration procedures, participant’s visits may be conducted over the phone at alternating time points (e.g. Months 2 and 4, or Months 3 and 5 visits can be over the phone. Visits done by phone will not have VS collected. The same is true of months 7-8 and months 10-11. The exception to this is for participants of childbearing potential who will need to be seen in-person for all study visits because a pregnancy test needs to be administered.
- ++ Participants will provide informed consent in two stages – consent for screening evaluation (ICF1), followed by consent for main study (ICF2) if eligible (see consent forms)
- +++ The mental health provider must provide concurrence after ICF 1 has been signed and prior to randomization. The primary care provider must be made aware of study participation prior to randomization.
- ++++ EKG will be performed on all participants at screening, at least once during titration and once when steady state has been achieved and at End of Study/Early Termination
- +++++ Study medication is only dispensed at end of study visits if a warm-hand off has been delayed.

Table 7: Study Flowchart for Participants Who Discontinue Study Medication

[figure not shown]
Study Activities	DISCONTINUE STUDY MEDICATION WITHOUT ACTIVE FOLLOW UP		DISCONTINUE STUDY MEDICATION WITH ACTIVE FOLLOW UP				
	At Early D/C Visit	At 30 Days F/U Visit	AT EARLY D/C VISIT	AT 30 DAYS F/U VISIT	DURING ACTIVE FOLLOW UP*	AT END OF STUDY VISIT	AT 30 DAYS F/U VISIT
Physical Exam (B01)	X		X				
Medications and treatments reviewed (S03)	X		X		X	X	
Vital Signs (B01, T04)**	X		X	X			
EKG (S09)	X		X				
Creatinine (S10, T02)	X		X				
CBC, electrolytes, calcium (S10, T01)	X		X				
TSH, T4 (S10, T02)	X		X				
Pregnancy test as appropriate (S10, T01)	X		X				
Service use based on the Cornell Service Index (B05)	X	X	X	X	X	X	X
Lithium level (T02)							
Adherence (T03, T05)	X		X				
Adverse events, (SAEs and AEs) (using lithium side effects checklist) (B13, T02)	X	X	X	X	X	X	X

Medications (S03)	X		X		X	X	
VA record review	X	X	X	X	X	X	X
SIS (S08)	X (as needed)	X (as needed)	X (as needed)	X (as needed)	X (as needed)	X (as needed)	X (as needed)
Columbia Follow up (B06)	X	X	X	X	X	X	X
PHG-9 (B07)	X	X	X	X	X	X	X
ISS (B08)	X	X	X	X	X	X	X
Audit C (B09)	X		X			X	
Follow up laboratory Information (T01)	X		X				

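### The early on-treatment blood-count, electrolyte, calcium and thyroid panel is tied to titration visit T4, which participants who finish titration at T2 or T3 never have

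*Protocol*

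**What the plan says.** Section XIII (Titrating study medication) keeps participants in titration until the lithium level is 0.6 to 0.8 mEq/L at two consecutive visits on the same dose, with the second level equal to the first or 0.1 lower. On how long this takes it says: "It is expected that most patients will titrate within 4-6 visits, but the process may take fewer visits, or may take up to 8". For anyone who gets there in under 60 days, the "next visit will be a steady state follow-up visit 2 months after randomization". Section XIV (Titration Visits) sets the spacing: "there is a window of 10 to 14 days between titration visits".

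Table 6 has two rows for this panel, one for blood count, electrolytes and calcium and one for TSH and thyroxine. (Thyroxine is also labelled T4 in the table; below, T4 always means the fourth titration visit.) During titration both rows are marked only at visit T4, and neither is marked in months 2 to 5. The EKG row of the same table is written differently, as "X (once during titration", and its footnote repeats that every participant has at least one tracing in that phase.

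Section XIV (Determination of lithium levels) counts thyroid function, blood counts and electrolytes within the close surveillance it treats as essential to safety. It gives no timing for them.

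**The concern.** A scheduled test tied to a numbered visit is done only if that visit takes place. The number of titration visits varies by design, and the rules allow titration to stop before T4. No footnote or text in the protocol moves the panel when that happens. A site that follows the published plan exactly would then run no routine thyroid, electrolyte, calcium or blood-count check between screening and month 6 in those participants. Early laboratory data would also be missing selectively, according to how fast a participant titrated. The primary endpoint, power and type I error are not affected.

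**Working it through.** **1. Where the marks fall.** Table 6 rows matched to visit columns by position:

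| Row | Screening (ICF 2) | T1 | T2-3 | T4 | T5-6 | M2-5 | M6 | M9 | Early D/C, end of study |
|---|---|---|---|---|---|---|---|---|---|
| Lithium level | | X | X | X | X | X | X | X | |
| Creatinine | X | X | X | X | X | X | X | X | X |
| Blood count, electrolytes, calcium | X | | | X | | | X | | X |
| TSH, thyroxine | X | | | X | | | X | | X |

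The table was extracted from PDF, so the alignment was checked in two ways. Visit times are 1.25 hours at T4 and M6 but 45 minutes at T2-3 and T5-6, which fits extra work at T4 and M6. The lithium row runs through M6 and then M9, which fits the monthly-then-quarterly schedule in Sections XIII and XIV.

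**2. Whether titration can end before T4.** Section XIII starts participants at 600 mg/day (300 mg if clinically indicated), steps by one 300 mg tablet, and assumes levels rise in proportion to dose. The minimum number of visits to confirm steady state is

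(final dose − starting dose)/300 + 2.

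- Start 600 mg, level 0.60 to 0.80 at T1: (600 − 600)/300 + 2 = 2, confirmed at T2.
- Start 600 mg, level 0.40 to 0.53 at T1: step to 900 mg, which gives 0.40 × 1.5 = 0.60 to 0.53 × 1.5 = 0.80. Then (900 − 600)/300 + 2 = 3, confirmed at T3.
- Start 600 mg, level below 0.40 at T1: needs 1,200 mg or more, so at least (1,200 − 600)/300 + 2 = 4, and T4 takes place.
- Start 300 mg: a level of 0.60 to 0.80 can be confirmed at T2. A level of 0.30 to 0.40 steps to 600 mg and can be confirmed at T3.

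These are minimums. A rise between the two levels, a held dose, a missed draw or a dose reduction adds visits.

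**3. Timing.** At 10 to 14 days per visit, T2 is day 20 to 28, T3 day 30 to 42 and T4 day 40 to 56. T2 and T3 are both under 60 days, so the next visit is month 2, which has no panel. Month 6 is about day 183 (365/2 = 182.5), or day 176 to 190 with the one-week window.

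- Delay against T4: 183 − 56 = 127 to 183 − 40 = 143 days.
- With the month-6 window: 176 − 56 = 120 to 190 − 40 = 150 days.
- If the first draw is on day 5 to 9, as Section XIII allows (day 7 ± 2), T4 is day 5 + 30 = 35 to 9 + 42 = 51, and the delay is 183 − 51 = 132 to 183 − 35 = 148 days.
- With the 5 to 7 day spacing in SAP section 3.2, T4 is day 20 to 28, and the delay is 183 − 28 = 155 to 183 − 20 = 163 days.

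**4. How many.** The documents give no share. Assuming 5% to 30% finish before T4: 0.05 × 1,862 = 93 and 0.30 × 1,862 = 559. Half of these, about 47 to 279, would be on lithium if early finishing is equally common in both arms.

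**The case against.** The best counter-argument is about intent. For the EKG the protocol says in words that everyone has one during titration, and it says nothing like that for the blood panel. The T4 mark could then be a deliberate check on those still titrating. But nothing in the documents gives a reason to exempt fast titrators, who are also taking study drug, and Section XIV names these tests as surveillance without any such limit.

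Second, no early harm is shown. Section XII (Side Effects and Adverse Reactions) reports raised TSH in about 30% and clinically significant thyroid decreases in 1% to 4%, without dating them to the first months. It cites calcium changes from long-term use. This stands: no number of delayed detections can be claimed.

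Third, monitoring continues. Creatinine, lithium levels and the side-effect checklist are scheduled throughout, and when events arise the Site Physician can "obtain blood for lithium level and other determinations as needed using the same procedures for planned dose adjustments". This stands as a limit on the harm. Testing prompted by an event does not replace a routine screen, though.

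Fourth, the 5% to 30% share has no anchor in the documents, and the rule that the second level must not rise makes very early finishing less common. This also stands; the range is an illustration.

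Finally, the Operations Manual and case report forms are not public and may cover the case. The finding applies to the published protocol and SAP only.

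**Conclusion.** The gap is real. Under the protocol's own rules, a participant confirmed at T2 or T3 has no scheduled blood count, electrolytes, calcium or thyroid tests from screening until month 6. The first on-treatment panel then comes about 127 to 143 days later than for someone who reaches T4 (120 to 150 with the visit window, and longer under the SAP's visit spacing). The number affected is unknown and probably a minority, because most participants are expected to need 4 to 6 visits. What is lost is one interim safety panel per affected participant, with renal and lithium monitoring intact. It is a modest point, worth correcting because the correction is cheap.

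**What to change.** In both panel rows of Table 6, replace the mark at visit T4 with the EKG row's wording, once during titration. Add a footnote: draw the panel at T4 or, if titration may end sooner, at the visit where the second level at an unchanged dose is drawn; if it is missed there, draw it at the first in-person steady-state visit.

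The trigger should be the second draw at an unchanged dose, because sites get the lithium result only about 3 days after blood shipment and cannot know at the visit that it is the last one. The fallback must specify in person, because the Table 6 footnote says "Months 2 and 4, or Months 3 and 5 visits can be over the phone".

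The cost is the footnote and a visit rule in the data-capture system covering the local order (blood count, electrolytes) and the central order (TSH, thyroxine). The rule must also cover calcium, which Section XIII assigns to neither laboratory. No visit is added, since blood for lithium and creatinine is already drawn at every titration visit. The added laboratory cost is one panel per affected participant, which the schedule already provides for everyone who reaches T4.

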Serious Adverse Events: All SAEs shall be collected for CSP #590 regardless of relatedness; however, the Site Investigator must still make an assessment of whether or not the event is related to the study intervention. All SAEs will be recorded on the appropriate case report form. SAEs that meet the criteria for an endpoint should be reported as such.

Adverse Event and Serious Adverse Event Monitoring

Patients will be actively monitored at each clinic visit and telephone contact for AEs and SAEs. All AEs and SAEs will be recorded on the appropriate event form(s). Per CSP policy, active and passive monitoring of AEs and SAEs will begin when a participant signs the Randomization Informed Consent. Monitoring of AEs and SAEs will continue through to 30 days past the “end of study” for each study subject. (No SAEs should be collected for participants after withdrawal of consent).

Expedited Reporting of Serious Adverse Events to CSP

All SAEs will be promptly reported by reporting the event via the CSP #590 Electronic Data Capture (EDC) system *within 72 hours* of the Site Investigator or other study personnel being made aware of the event. Email notification of the submission is relayed by the EDC system to the study Biostatistician, Clinical Research Pharmacist, Study Director, and Study Chair. The CSP #590 Clinical Research Pharmacist (CRP) is responsible for evaluating all SAEs for immediate patient safety concerns. A back-up CRP will evaluate the event in if the primary CRP is not available.

Reporting of Serious Related and Unexpected Events

The determination of the expectedness of an event is the responsibility of the CSP. The source of information used in the determination of expectedness includes the CSP #590 Drug Information Report, the Informed Consent form, and published literature. SAEs determined by the CSP to be both related to the study intervention and unexpected after review by the CRP, the Study Chair, and consultants as needed will be reported to the VA Chief Research and Development Officer, the FDA, and site investigators.

Reporting of Adverse and Serious Adverse Events to the DMC

The Coordinating Center and CSPCRPCC will summarize blinded and unblinded AE and SAE data for the DMC in a format and on a schedule requested by the DMC. The DMC will receive results by treatment group (e.g. A versus B) but will not receive fully unblinded reports until all data collection has been completed.

Reporting Requirements of the VA Central IRB

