7.4. Safety Data

Safety information to be collected for this study include description of the event, distinction between serious and non-serious adverse event, severity and expectedness of the event, relatedness to the study intervention, and outcome of the event. In addition, data on all events will be classified using the Medical Dictionary for Regulatory Activities (MedDRA) (Version 9.0) coding dictionary.

Safety data will be collected for all consented subjects from the date the first consent was signed up to 13 months post randomization for related non-serious adverse events, and all serious adverse events. If the subject terminates from the study prior to 13 months post randomization date, collection of safety data will cease on termination date.

For reporting to the DMC and inclusion in the final report safety data will be aggregated for the ITT analytic sample only as described in **3.3**. Data will be summarized as follows.

- Frequency and percentages of related non-serious and all serious adverse events overall and by intervention group
- Frequency and percentages of all unique subjects with non-serious and serious adverse events overall and by intervention group
- Rates of non-serious and serious adverse events overall, by intervention group, and by center, calculated as # events/ person-time in years
- Tabulation of event type, MEDRA classification, severity, expectedness, relatedness and outcome of all events overall and by intervention group
- Overall hospitalization, suicide reattempt, and mortality rates at 1 year overall and by intervention group

8. Data Monitoring Committee Reports

Data and study progress will be monitored by the study executive committee and by the Data Monitoring Committee (DMC). The DMC will review the study progress and safety semi-annually with additional meetings and communications as needed. All reports will be generated using SQL and SAS.

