8.3.5. Section D: Safety Assessment (CLOSED SESSION ONLY)

Table D1. Rates of Non-Serious Related Adverse Events (NAEs), by Site and Treatment
Table D2. Rates of Serious Adverse Events (SAEs), by Site and Treatment
Table D3. **Reported in OPEN SESSION only**
Table D4. Summary of Serious Adverse Events (Form B15), by Treatment
Table D5. Related Non-Serious Adverse Events by System Organ Class, by Treatment
Table D6. Serious Adverse Events by System Organ Class, by Treatment
Table D7. Deaths Reported, by Treatment

9. Analytic Tables not included in the Data Monitoring Committee Reports

Following analytic tables will be generated annually and made available to the study team, Upon request of the DMC at the initial meeting these tables will not be included in the DMC report.

Table X1. Military Service

Table X2. Medical and Psychiatric History

Table X3. MINI Module Assessment

Table X4. Baseline Physical Assessments

Table X5. Baseline Laboratory Results

Table X6. Baseline Psychiatric Measures

Table X7. Baseline Substance Use (SCID-SUD)

Table X8. Concomitant Medications

10. Sample Size and Power

CSP590 is targeted to enroll a total of 1862 subjects, and approximately 40% of the enrolled sample is expected to terminate early (i.e., 20% complete data loss), thereby resulting in an analytic sample of 1490 evaluable subjects. With the evaluable study sample equally allocated to the 2 treatment arms, the study is powered to detect at least a 37% reduction in the one year outcome event rate.

Expected event rates used in sample size estimation to achieve 90% statistical power for hypothesis testing were 15% re-attempt rate in the placebo group and 9.45% re-attempt rate in the lithium group. Justification for selecting these rates to estimate sample size and power are provided in the protocol.

The results for the primary outcome measure will be analyzed by a two-sided log-rank test to detect either a hazards ratio that exceeds $1/0.61=1.64$ or is less than 0.61, i.e., the test has 90% power to detect a hazard ratio of 1.64 or larger or 0.61 or less.

These estimations are adjusted for an O'Brien-Fleming stopping rule with one interim and one final test of hypothesis, and allow for an overall two-sided type I error of 5% for the hypothesis being tested. Hence, the interim primary hypothesis will be tested at $p=0.002$ level (allowing for 0.2% Type I error), and the final primary hypothesis will be tested at $p=0.048$ level (allowing for 4.8% Type I error).

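### After a participant's death, other serious adverse events still open are to be closed as resolved, which would misstate their outcome in the by-arm safety tabulation

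*Protocol*

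**What the plan says.** Protocol Section XIV, under the heading on notifications and procedures after a participant's death, has a procedures table. Its row on completing SAE forms names study staff at the pharmacy coordinating centre as responsible. The entry in the recommendation column reads: "Any other outstanding SAE forms should be closed out with the resolved option". The row makes no exception for an event that was ongoing, worsening or contributory at death. It does not ask for evidence of resolution, and it names no other closing category.

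Protocol Section XV sets the scope of collection: "All SAEs shall be collected for CSP #590 regardless of relatedness".

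SAP 7.4 lists the safety items to be collected, ending with "relatedness to the study intervention, and outcome of the event". It says where they go: "For reporting to the DMC and inclusion in the final report safety data will be aggregated for the ITT analytic sample only". Among the planned summaries is this one: "Tabulation of event type, MEDRA classification, severity, expectedness, relatedness and outcome of all events overall and by intervention group".

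SAP 8.3.5 lists the closed-session tables for the Data Monitoring Committee (DMC). They include "Table D4. Summary of Serious Adverse Events (Form B15), by Treatment" and "Table D7. Deaths Reported, by Treatment".

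**The concern.** A form is outstanding because the event has not been followed to an end. Death stops the follow-up but does not show that the event resolved. The rule assigns the favourable value by default, and only for participants who died.

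The same procedures table treats cause of death differently, asking that it be established from medical records or the death certificate. No comparable check is required for the outcome of the other open SAEs.

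What is at stake is the accuracy of one safety attribute that the SAP plans to compare between arms. Because the misclassification is triggered by death, it need not be equal in the two arms. The protocol lists excessive SAEs or mortality in either group among the grounds on which the DMC may consider early termination (Section XVII), so the safety tables should be right in the participants with the worst course.

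**Working it through.** The plan states no figure on this point, so there is none to reproduce. The check sets the passages side by side and then gives a scale.

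**Step 1: which events fall under the rule.** Section XV collects all SAEs whatever their relation to treatment. The rule covers forms other than that of the fatal event, so it applies to non-fatal SAEs still open when the participant died.

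**Step 2: what value they receive.** The procedures table says resolved, with no condition attached.

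**Step 3: where that value goes.** SAP 7.4 collects the outcome of each event and tabulates it by arm for the DMC and the final report. I found nothing in either document that recodes a closure made because of death or shows it separately.

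**Step 4: the inferred link.** The form's option list is not in the documents. That the resolved option fills the tabulated outcome field is therefore an inference. It is the natural one, since resolved is ordinary outcome vocabulary and outcome is a collected item. If the option is only an administrative form status, the effect on the outcome tabulation would be smaller.

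**Step 5: what is not touched.** The rule changes neither the number of SAEs nor their organ class. In SAP 8.3.5, SAE rates by site and treatment (Table D2), SAEs by organ class (Table D6) and deaths by treatment (Table D7) stand as they are. The fatal event keeps its own form. The primary endpoint is unaffected.

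**Step 6: scale, for illustration only.** For one arm,

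misclassified SAEs = deaths × share of decedents with another open SAE × open SAEs per such decedent.

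The documents give none of these for trial participants. The nearest input is one-year all-cause mortality of about 3–5% among VA attempt survivors (Protocol Section I).

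- On 1,862 randomised: 1,862 × 0.03 = 56 and 1,862 × 0.05 = 93 deaths, or about 28 to 47 per arm if balanced.
- On the 1,490 effective participants: 1,490 × 0.03 = 45 and 1,490 × 0.05 = 75 deaths.

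The share with another open SAE is purely an assumption:

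| Assumed share | Decedents affected, N = 1,862 | Decedents affected, N = 1,490 |
|---|---|---|
| 10% | 6–9 | 4–7 |
| 25% | 14–23 | 11–19 |
| 50% | 28–47 | 22–37 |

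These are upper-end figures. The mortality comes from an unselected population, whereas the trial excludes heart failure, estimated GFR below 60 and prolonged QTc (Protocol Section V). About 40% dropout is planned for, and SAP 7.4 stops safety collection at termination. The table shows how far the count depends on an unknown share. It does not estimate the count.

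**The case against.** The strongest reply is that the sentence concerns form administration. It says how to close forms, the form itself is not shown, and the resolved option might be a status flag. It is also worded as a recommendation rather than a requirement. All of that is fair, and it is why the conclusion is conditional on the reading in Step 4. It does not dispose of the point, because this is the only instruction staff are given, and neither document says that the option is something other than the event's outcome.

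A second reply is that the important information survives elsewhere. This stands. A reader might infer that the rule hides a lithium safety pattern from the DMC. The documents do not support that. A renal, cardiac or toxicity SAE would still be counted by arm and organ class, and an excess of deaths would show directly in Table D7. Section XV also has the clinical research pharmacist evaluate every SAE for immediate safety concerns, with reporting due within 72 hours. What those tables do not do is correct the outcome recorded for the decedent's other SAEs.

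A reader might also infer that Table D4 will display the wrong outcomes. Only its title is given, and SAP 8.2 keeps the table shells in a separate file. The general outcome tabulation in SAP 7.4 is the firm basis.

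Finally, it is tempting to state a number of falsely resolved SAEs. Any such number rests on an unanchored share and on mortality in a different population.

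**Conclusion.** The instruction is wrong as written. It records resolution where none has been shown, and SAP 7.4 tabulates event outcome by arm with nothing to undo this. The conclusion assumes that the resolved option populates the SAE outcome field. The direction is known: outcomes look more favourable than they were among participants who died. Any difference between arms depends on whether deaths or open SAEs differ by arm, which cannot be known in advance.

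The size is limited to one attribute of non-fatal SAEs open at death, and the number of events cannot be derived from the documents. No SAE count or rate, organ-class table, mortality comparison or efficacy analysis changes. The point merits correction because it is plain and cheap to fix. It does not call the wider safety reporting into question.

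**What to change.** Replace the sentence in the death-procedures table with: *Other outstanding SAEs are closed as not resolved/ongoing at death (or unknown); resolved is used only where source records show resolution before death.*

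Keep the fatal outcome on the fatal event's own form only. Coding another SAE as fatal because it contributed to the death could record one death under two SAEs.

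In SAP 7.4, show the ongoing-at-death category as a separate row, by arm, in the outcome tabulation. If the resolved option turns out to be only a form status, say so in the table and state how the outcome field is completed for these events.

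The cost is one line of protocol text, possibly one new outcome code on the SAE form, and SAE outcomes that read slightly less favourably. This is a data-coding change and leaves clinical management as it is.
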